#### 6.6.4 Inflammatory mediator analysis:

Plasma and sputum markers will be assessed by commercial ELISA: CRP, IL-6, IL-8, TNF $\alpha$  (R&D). Plasma CRP will be analysed using a high-sensitivity commercial ELISA assay (MP-Biomedicals, Santa Ana, California, USA) as per the manufacturer's instructions. The sensitivity for this assay is 5ug/L. Plasma IL-6 will be analysed using a high-sensitivity commercial ELISA assay (R&D Systems, Minneapolis MN USA) as per the manufacturer's instructions. The sensitivity for this assay is 0.7pg/ml. Plasma TNF- $\alpha$  will be analysed using a high-sensitivity commercial ELISA assay (R&D Systems, Minneapolis MN USA) as per the manufacturer's instructions. The sensitivity for this assay is 5.5pg/ml. All samples will be tested in duplicate.

#### 6.6.5 Gene expression analysis

RNA will be extracted from sputum cells and PBMCs using RNeasy Mini Kit (Qiagen, Hilden, Germany) and quantitated using the Quant-iT RiboGreen RNA Assay Kit (Molecular Probes Inc, Invitrogen, Eugene, OR, USA) as per manufacturer's instructions. RNA is then converted to cDNA using High Capacity cDNA Reverse Transcription Kit (Applied Biosystems, Foster City, CA, USA) via standard Taqman methods. Taqman qPCR primer and probes for HDAC subtypes (1-11), GPR43 and GPR41 are combined with cDNA Taqman gene expression master mix as per manufacturer's instructions in duplicate real-time PCR reactions (7500 Real Time PCR System: Applied Biosystems). Analysis is performed on the change in cycle threshold ( $\Delta$ Ct) between the target gene compared with the housekeeping gene 18S rRNA, calculated using  $2^{-\Delta\Delta$ Ct} relative to 18S and the mean of the baseline value .

### 6.6 *Statistical Analysis*

Analysis will be performed with STATA 15 (StataCorp, College Station, Texas, USA) and reported as mean  $\pm$  standard deviation or median [interquartile range]. Within group comparisons of outcomes compared to baseline will be assessed using the student t-test or Wilcoxon signed-rank tests. Per protocol analysis of mean difference in outcomes between treatments will be tested using mixed model regression, accounting for repeated measures. An independent ANOVA of period totals by treatment sequence will be used to test the assumption of no carry over effects. Associations will be assessed using Spearman's correlations. Significance will be accepted if  $p < 0.05$ .

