#### Randomisation

All participants will receive both treatments and the placebo. Treatment order will be randomly allocated via unique randomisation codes using a 3x3 latin square method  by an

independent statistician. The randomisation service will be managed by an independent statistician at the Hunter Medical Research Institute.

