## Study Visits

Participants will be screened for study eligibility by telephone prior to study commencement, and will then attend a screening visit where they will have a brief medical examination, dietary questionnaire, have their blood pressure, weight and height measured. If no abnormalities or exclusion criteria are identified, they will be entered into the study. They will commence the study background diet for 2 weeks, then attend the HMRI clinic on 6 occasions, before and after each 7 day intervention (inulin, inulin+probiotic and placebo), which will be separated by 2 weeks (Figure 4). During each intervention phase, participants will be telephoned for motivational purposes, to record compliance with the intervention, the study diet, and to establish whether any adverse effects have been experienced.

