### Study diet

For 2 weeks prior to the first visit and for the duration of the study, participants will be instructed by a study dietitian to consume a fibre-controlled background diet. This will be achieved by avoidance of soluble fibre-rich foods including oats, oat bran, beans, seeds and limiting fruit and vegetable intake to no more than 2 serves/ day. Participants will be instructed to consume ½ cup of bran-based cereal (45g serve contains 1.5g soluble and 11.8g insoluble fibre) daily to ensure adequate total fibre intake. Subjects will also be instructed to avoid sources of probiotics such as yoghurt and fermented milk drinks and sources of inulin such as asparagus and artichokes. We will explain to subjects that they can consume all other foods including 2 serves of fruit or vegetables as usual.

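### Within-arm tests against baseline have no placebo control and carry any time trend in full; the between-treatment model should name period and say how each period's pre-treatment value enters

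*Protocol*

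**What the plan says.** Section 6.6 Statistical Analysis sets out two kinds of comparison. The first is inside each arm: "Within group comparisons of outcomes compared to baseline will be assessed using the student t-test or Wilcoxon signed-rank tests". The second is between arms: "Per protocol analysis of mean difference in outcomes between treatments will be tested using mixed model regression, accounting for repeated measures". One threshold, p < 0.05, closes the section and applies to both. The section does not call the within-arm tests descriptive. It also does not say whether baseline means visit 2 or the visit that opens each period. The only other item specific to the crossover is a carry-over check: "An independent ANOVA of period totals by treatment sequence will be used to test the assumption of no carry over effects".

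The design supplies more than this text uses. Under Study Visits (section 6.3), participants will "attend the HMRI clinic on 6 occasions, before and after each 7 day intervention", and the list for visits 2 to 7 is the same at every visit. Order is allocated "using a 3x3 latin square method" (section 6.1, Randomisation). On the fibre-controlled background diet, section 6.3 says: "For 2 weeks prior to the first visit and for the duration of the study, participants will be instructed by a study dietitian".

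Pre-treatment values do appear elsewhere. Section 6.6.3(c) measures microbiota change between paired samples taken before and after treatment, and section 6.6.5 scales gene expression to the baseline mean.

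**The concern.** A before/after test inside one arm answers a different question from the trial's. It cannot separate the supplement from time on the diet, regression to the mean or learning effects. The usual misuse is to read a significant change in an active arm beside a non-significant change on placebo as evidence of efficacy. The protocol lists many secondary outcomes, so there are many chances for that pattern to appear.

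The comparison that does use the placebo is described in one phrase. Two pieces of information that the design provides, the period and the value at the start of each period, are not mentioned in it. If they were left out, precision could be lost. If the sequences also ended up unequal, part of any drift would enter the treatment contrasts. The number of participants cannot be split equally over three sequences, since 17 is not a multiple of 3. Dropout (10% allowed in section 6.7) and exclusion below 80% adherence (section 6.1) could widen the imbalance.

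**Working it through.** The protocol gives no drift and no correlations, so those inputs are assumed and shown as ranges.

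**1. The plan's own figure.** Section 6.7 states 90% power with n = 15, a 1 SD change and alpha 0.025. A paired t-test with 14 degrees of freedom, noncentrality 1 × √15 = 3.87 and two-sided alpha 0.025 gives power 0.898. Then 15 / 0.9 = 16.7, so 17. The figure reproduces as a plain paired comparison with no period or baseline term.

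**2. Within-arm tests.** Take n = 15, two-sided alpha 0.05, no treatment effect, and a common drift δ in units of the SD of the change. The rejection probability p in one arm comes from the noncentral t with noncentrality δ√15. If changes are independent between arms, the chance that at least one active arm is significant while placebo is not is (1 − (1 − p)²)(1 − p).

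| δ | p, one arm | active significant, placebo not |
|---|---|---|
| 0 | 0.05 | 0.09 |
| 0.2 | 0.112 | 0.19 |
| 0.3 | 0.192 | 0.28 |
| 0.5 | 0.438 | 0.38 |

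For δ = 0.3: (1 − 0.808²) × 0.808 = 0.347 × 0.808 = 0.28.

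**3. Period and bias.** Take sequences ABC, BCA, CAB, a linear drift of d per period (0, d, 2d), and no period term. The mean drift carried by each treatment is:

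- 5/5/5: d for all three treatments, so every contrast is unbiased.
- 6/6/5: A 17/17, B 16/17, C 18/17 of d. Contrast biases are 1/17 = 0.06d (twice) and 2/17 = 0.12d.
- 6/6/3: A 15/15, B 12/15, C 18/15 of d. Contrast biases are 0.2d (twice) and 0.4d.

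Which contrast takes the largest bias depends on which sequence is short.

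**4. Period and precision.** Take 15 completers split 5/5/5 and d in within-person error SDs. Without a period term the residual has 28 degrees of freedom, and its expected mean square rises by the factor 1 + (15 × 2d²)/28. The SE is therefore multiplied by 1.03 at d = 0.25, 1.13 at d = 0.5 and 1.44 at d = 1. A simulation (4000 runs per setting, true difference 1 SD of the paired difference, alpha 0.025) gives:

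| d | power without period | power with period |
|---|---|---|
| 0 | 0.92 | 0.92 |
| 0.5 | 0.88 | 0.93 |
| 1.0 | 0.68 | 0.93 |

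Without the term and with drift, type I error falls below 0.025 (0.015 at d = 0.5), so in the balanced case the error is conservative.

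**5. Pre-treatment value.** Let b be the correlation between values from different periods and w the pre-post correlation within a period. After participant effects are removed, r = (w − b)/(1 − b). Relative to using post-treatment values alone, the contrast variance is 1 − r² with covariate adjustment and 2(1 − r) with change scores. With b = 0.5:

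| w | r | covariate | change score |
|---|---|---|---|
| 0.5 | 0 | 1.00 | 2.0 |
| 0.6 | 0.2 | 0.96 | 1.6 |
| 0.7 | 0.4 | 0.84 | 1.2 |

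Against the planned 0.90, power is 0.90, 0.91 and 0.94 with the covariate, and 0.60, 0.71 and 0.83 with change scores.

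**The case against.** The strongest reply is that silence is not exclusion. Fixed effects, covariates and degrees-of-freedom methods are commonly left to a statistical analysis plan, and that plan may exist. The carry-over ANOVA shows that the authors had the crossover structure in mind. This stands: the protocol cannot be charged with having dropped period or baseline. The carry-over check, however, does not replace a period term.

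The second reply is that the Latin square already protects the treatment contrasts. This also stands. Common drift cancels when sequences are equal, the 6/6/3 split needs both losses to fall in the sequence that is already short, and a two-week diet run-in should reduce early drift.

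The third reply is that the gain from baseline may be small, because the participant effect already absorbs stable differences between people. This stands too. A residual r of 0.7, which would save about half the variance, would need an ordinary pre-post correlation of 0.85 when b = 0.5.

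Last, a between-treatment model is planned, and nothing says that efficacy will be concluded from the within-arm tests. That is true. But the protocol does plan those tests as tests, under the same p < 0.05 rule, with no descriptive label and no definition of baseline. That is stated text, not an omission that a later plan would be expected to fill.

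**Conclusion.** The point holds in a limited form. The firm part is the within-arm testing. It is planned explicitly, has no control, and carries any drift in full. Under the assumed drifts of 0.2 to 0.5 SD of the change, the false-positive rate in an arm is 0.11 to 0.44 instead of 0.05.

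The softer part is that the between-treatment model should name period and the period-specific pre-treatment value. The cost of leaving out period is none without drift, about 5 points of power at 0.5 within-person SD per period, and about 25 points at 1 SD. Bias needs unequal sequences and is 0.06 to 0.12 of the per-period drift at the best split of 17. The gain from baseline is about 0 to 16% of variance under the assumed correlations.

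A reader might infer that the plan compares treatments without period or baseline, and that diet-related drift therefore sits in the treatment result. The documents do not support this: the model text is silent, not exclusive, and the Latin square removes common drift apart from imbalance. Nor can one say that baselines serve only the within-arm tests, given their use for microbiota and gene expression, or that the sample size is wrong.

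**What to change.** In section 6.6 Statistical Analysis:

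- State the between-treatment model as the post-treatment value on treatment and period (fixed effects), with that period's pre-treatment value as a covariate, not as a change score, and participant as the repeated unit.
- With participant as a random effect, a single covariate blends the between-person and within-person relations. Adding the participant's mean pre-treatment value, with a small-sample degrees-of-freedom method such as Kenward-Roger, is one reasonable choice among several. Say which is used.
- Define baseline.
- Base all conclusions on the between-treatment contrasts. Report within-arm changes with estimates and spread, without significance tests.

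The data are already collected at visits 2 to 7, so the change is one of wording. It costs a few degrees of freedom: two for period and one or two for baseline. In the simulation without drift, adding period left power at 0.92. The sample size in section 6.7 need not change.

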### 6.7 *Sample size calculation*

Based on previous studies , we hypothesise that we would observe a change in plasma acetate of  $\sim 1$ SD. With  $n=15$  subjects, we would have 90% power to detect a difference between groups, using  $\alpha=0.025$  (to avoid type 1 error when comparing 3 groups).

Allowing for 10% dropouts, we aim to recruit n=17 subjects.

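### The trial is sized at alpha 0.025 to protect against multiplicity, but the analysis section accepts significance at p < 0.05 with no exception for the primary outcome

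*Protocol*

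**What the plan says.** The design is a three-period crossover of inulin, inulin+probiotic and placebo (protocol, Synopsis and section 6.1). The primary outcome is plasma SCFA (section 6.4).

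- **Section 6.7, Sample size calculation.** The planning assumption is "we hypothesise that we would observe a change in plasma acetate of $\sim 1$ SD". On 15 subjects and an alpha of 0.025, the protocol states that "we would have 90% power to detect a difference between groups". The reason given for that alpha is "to avoid type 1 error when comparing 3 groups". Recruitment is set at 17 to allow for 10% dropout.
- **Section 6.6, Statistical Analysis.** The between-treatment analysis is described thus: "Per protocol analysis of mean difference in outcomes between treatments will be tested using mixed model regression, accounting for repeated measures". The section closes with a single criterion, "Significance will be accepted if" p < 0.05. It gives the primary outcome no separate level and mentions no adjusted p-values, hierarchy or preliminary overall test.
- **Section 6.6.3(c), Faecal microbiota.** The PERMANOVA has its own level, 0.01. So the protocol does name a different level where it wants one.

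**The concern.** Section 6.7 recognises that comparing several treatments inflates the type I error and chooses a smaller alpha for that reason. The false-positive rate, however, is set by the threshold applied to the data, and that threshold is in 6.6. There it is 0.05.

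Two things are at stake. First, the error rate on the primary question is higher than a reader of 6.7 would expect. Second, if a primary contrast gives a p-value between 0.025 and 0.05, 6.6 calls it significant, while a reader of 6.7 would expect it to miss the threshold. That should be settled before the data are seen.

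**Working it through.** **Inputs.** From section 6.7: effect about 1 SD, n = 15, alpha 0.025, power 90%, dropout 10%, recruited n = 17. From section 6.6 (Statistical Analysis): criterion p < 0.05. From the design: two active treatments and one placebo, all given to every participant. Two assumptions are needed because the protocol does not state them: tests are two-sided, and 1 SD means the SD of the within-subject difference.

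**Step 1. Reproduce the stated power.** Paired t-test with n − 1 = 14 df and noncentrality d√n = 1 × √15 = 3.873.

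- Two-sided 0.025: critical t = 2.510, power **89.8%**, which matches the stated 90%.
- Two-sided 0.05: critical t = 2.145, power 94.9%.
- One-sided 0.025: power is also 94.9%, which does not match.

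The 0.025 in 6.7 therefore behaves as a two-sided level equal to 0.05/2, the Bonferroni level for two comparisons. It is not shorthand for a one-sided test. The dropout allowance also agrees: 15/0.90 = 16.7, rounded up to 17.

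**Step 2. Family-wise error for the two active-vs-placebo contrasts on one variable.** If the two tests were independent, the rate would be 1 − (1 − α)²:

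- α = 0.05: 1 − 0.95² = 9.75%
- α = 0.025: 1 − 0.975² = 4.94%

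The contrasts share the placebo period, so they are positively correlated and the true rate is somewhat lower. It was simulated under no treatment effect: 300,000 trials, 15 completers, equal correlation between periods, pooled within-subject error on 28 df, no period or carry-over effects.

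| Level per contrast | Simulated | Independence |
|---|---|---|
| 0.05 (section 6.6) | 9.1% | 9.75% |
| 0.025 (section 6.7) | 4.6% | 4.94% |

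With separate paired t-tests instead of pooled error, the simulated rates are 9.2% and 4.7%. The answer does not hinge on that choice.

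**Step 3. Power once 0.025 is carried into the analysis.** It is the figure from step 1: 89.8% at n = 15, and 93.9% if all 17 complete. Nothing is lost against the plan, because the plan was sized at this level.

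**Step 4. Sensitivity of power to the meaning of 1 SD.** If 1 SD is instead the SD between subjects, the SD of the difference is √(2(1 − ρ)) times that SD, where ρ is the correlation between periods. Power at two-sided 0.025 with n = 15 is then 59.9% (ρ = 0), 76.8% (0.3), 89.8% (0.5) or 98.9% (0.7). The error rates in step 2 do not depend on this assumption.

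**The case against.** **A sample size section is not a decision rule.** This is right: 6.7 by itself never makes a result negative. A reader might infer that the two sections strictly exclude each other, but a trial can be planned at one level and tested at another. What cannot be kept is the reason given in 6.7, because a planning alpha protects nothing unless the analysis uses it.

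**Section 6.6 could mean an overall treatment test at 0.05, or adjusted p-values judged at 0.05.** An overall F test at 5% before the pairwise tests would hold the error near 5.0% when no treatment differs. But 6.6 mentions neither device. This reading has to be supplied by the reader and should be written down if it is meant.

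**The statistical analysis plan may settle it.** It may, and the choice of contrasts is a detail commonly left there. Unnamed contrasts alone would not be a fault. The mismatch between two adjacent sections of the protocol does not depend on the unseen document.

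**A stronger reading is tempting.** Because 6.7 speaks of three groups, a reader might infer three primary pairwise contrasts, a required level of 0.0167, an error rate of 12% and power of only 86%. The documents do not support this.

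- No three-contrast family is declared. A placebo-controlled design with two active treatments points to two contrasts, for which 0.025 is the Bonferroni level.
- Even for three contrasts, 0.0167 is sufficient but not necessary.
- The 86% is a paired-t figure on 14 df. With pooled error on 28 df, closer to the mixed model in 6.6, power at that level is 89.9%.

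**The consequence is modest.** Under the design assumption, p falls between 0.025 and 0.05 on a given contrast about 5% of the time (94.9% − 89.8%). Under the null it does so 2.5% of the time. That stands, and it limits the practical weight of the point, but the intended error control is still lost.

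**Conclusion.** The point holds. Section 6.7 claims protection against multiplicity at 0.025, and section 6.6 as written does not apply it. For two active-vs-placebo contrasts on one primary variable, the family-wise error is about 9% under 6.6, against about 4.6% under the level assumed in 6.7, so it is roughly doubled.

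The error rates assume two-sided, unadjusted tests of these two contrasts with 15 completers. The statement that power stays at about 90% further assumes that 1 SD is the SD of the within-subject difference.

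The rates apply to one variable only. Section 6.6.2(b) quantifies acetate, propionate and butyrate, while 6.7 powers acetate alone. The 9% should therefore not be read as a rate for the whole trial, and 0.025 per contrast gives the stated control only if one SCFA is named as primary.

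**What to change.** In section 6.6 (Statistical Analysis), state that:

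- the primary comparisons are inulin vs placebo and inulin+probiotic vs placebo on plasma acetate, the variable powered in 6.7, each tested two-sided at 0.025 (or by Holm at an overall two-sided 0.05);
- inulin vs inulin+probiotic, and the other plasma SCFAs, are secondary;
- p < 0.05 is a nominal level for secondary and exploratory outcomes.

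In section 6.7, replace the reference to three groups with two comparisons with placebo, and say that the level is two-sided and that 1 SD refers to the within-subject difference.

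The cost is a few sentences. The sample size stays at 17 recruited and 15 evaluable. The only downside is a stricter threshold on the primary outcome, which the sizing already assumes.

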## **7. Safety and ethical considerations**

### *10.1. Safety*

The conduct of the study will be in accordance with the Code of Good Clinical Practice (GCP) and the NHMRC National Statement of Ethical Conduct in Research. The Investigators and study personnel will meet regularly to monitor recruitment, progress, adverse events and data entry throughout the study.

Participants will be questioned by study personnel at each visit and during each phone call regarding any adverse symptoms related to consuming the study supplement.

Some clinical assessments performed during this research can be associated with adverse effects. Participants will be closely monitored while undergoing testing. Only qualified staff who are fully trained in the operation of equipment, clinical procedures and response to emergencies will complete evaluations.

Any adverse/abnormal results prior to or during the study will be reported to the CI and to the participants' GP (with the participants permission) to ensure appropriate follow up, with any severe adverse events to be reported to the HNEHREC within 72 hours (see 'Reporting of Adverse Events' section).

The side effects of having blood collected may include bleeding or bruising at the insertion site and possible dizziness and/or fainting. The saline challenge and sputum induction test can cause coughing, some minor chest discomfort and wheezing. This is brief and promptly responds to reliever medication, which will be provided for participants. The study supplement contains ingredients that are approved foods and considered safe and suitable for use in food in Australia. Some subjects may experience mild side effects of flatulence, bloating, cramps or loose stools, for 12-24 hours after consuming the study supplements.

With the participant's permission, abnormal findings from routine clinical tests will be forwarded to their GP for follow up.

### *10.2. Reporting of Adverse events*

An Adverse Event (AE) is defined as any untoward medical occurrence in a participant during the assessments conducted at each clinic visit and during the study intervention that may or may not be related to the study protocol and/or study supplement. A Serious Adverse Event (SAE) is defined as any untoward serious medical occurrence at any dose that results in death, or is life-threatening or requires inpatient hospitalisation, or results in persistent or significant disability/incapacity, or is a congenital anomaly/birth defect, or is a medically

important event or reaction.

The study coordinator will inform the principal investigator of all AEs and SAEs, who will then follow procedures as necessary and notify the relevant bodies. Depending on the nature of AE or SAE, it may be necessary for treatment to cease and/or for the participant to be withdrawn from the study.

All SAE's that may be related or unrelated to the study supplement will be documented in the SAE Form, Case Report Form and will be reported within 72 hours to the Human Research Ethics Committee, the sponsor and the TGA. Any unforeseen AE, or complaints from participants in the research, or about the research, will be documented in the AE Form and Case Report Form and will be reported to the Human Research Ethics Committee.

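### The AE definition covers any untoward event, but the visit question and the AE Form rule are narrower, so foreseen non-serious events need not enter the AE record

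*Protocol*

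**What the plan says.** **Definition (Protocol, 10.2).** An AE is "any untoward medical occurrence in a participant during the assessments conducted at each clinic visit and during the study intervention", and the definition adds "that may or may not be related to the study protocol and/or study supplement". Neither causality nor expectedness limits it.

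**Enquiry.** Section 10.1 has staff question participants at every visit and every phone call "regarding any adverse symptoms related to consuming the study supplement". Study Visits (section 6.3) has participants phoned in each intervention phase, among other reasons "to establish whether any adverse effects have been experienced", with no limit to related effects.

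**Recording (10.2).** All serious adverse events (SAEs), related or not, go on the SAE Form and the CRF. For non-serious events the rule is "Any unforeseen AE, or complaints from participants in the research, or about the research, will be documented in the AE Form and Case Report Form"; the same sentence also sends them to the ethics committee. Separately, "The study coordinator will inform the principal investigator of all AEs and SAEs".

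**Foreseen effects (10.1).** "Some subjects may experience mild side effects of flatulence, bloating, cramps or loose stools", expected to last 12 to 24 hours. The saline challenge may cause cough, minor chest discomfort and wheeze, described as brief. Blood collection may cause bleeding, bruising, dizziness or fainting.

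**Expedited reporting.** Section 10.1 deals "with any severe adverse events to be reported to the HNEHREC within 72 hours" and refers the reader to the section on reporting of adverse events. That section applies the same 72 hours to *serious* events and names the ethics committee, the sponsor and the TGA as recipients.

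**The concern.** An AE definition that ignores causality and expectedness works only if enquiry and recording follow it. Here each applies a filter first.

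- The question in 10.1 builds relatedness into what the participant is asked, so attribution is made before anything is written down.
- The form rule in 10.2 admits non-serious events only if they were unforeseen or reach staff as a complaint.

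The gastrointestinal effects that the protocol itself expects from the supplements are the natural basis for comparing tolerability between inulin, inulin plus probiotic and placebo. If those effects need not reach the AE Form, a low or similar AE count across treatments could reflect the recording rule rather than tolerability. A later analysis plan cannot restore events that were never put on a form.

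**Working it through.** There is no figure in the plan to reproduce. The check sets the sections against each other.

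**Step 1: does the question match the definition?** At visits, the only AE question stated is the one in 10.1, which is limited to supplement-related symptoms. The definition has no such limit, so the two differ. For calls during an intervention phase, staff hold two instructions: the restricted one in 10.1 and the open one under Study Visits. These conflict.

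**Step 2: does the form rule match the definition?** Non-serious AEs reach the AE Form and CRF if unforeseen or raised as a complaint. No sentence requires a form for a foreseen, non-serious AE. Informing the principal investigator of all AEs is notification; it does not itself create a form entry.

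**Step 3: which events fall in the gap?** Section 10.1 names 4 + 3 + 4 = 11 foreseen effects.

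| Events | AE Form required when non-serious? | Captured elsewhere |
|---|---|---|
| Flatulence, bloating, cramps, loose stools | Not stated while as foreseen | GSRS at visits 2–7: items on stomach pain, bloating, flatus, diarrhoea and loose stools, each scored 1–7 over the past week |
| Cough, chest discomfort, wheeze from the challenge | Not stated while as foreseen | FEV1 after each saline period; the ACQ asks about the past week, not about the challenge |
| Bleeding, bruising, dizziness, fainting from blood collection | Not stated | Neither questionnaire covers these |
| Infection, asthma worsening (not on the foreseen list) | Yes, if regarded as unforeseen, but the visit AE question does not prompt for them unless attributed to the supplement | ACQ and spirometry for asthma; neither questionnaire asks about infection |

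So 0 of the 11 named effects have a stated AE Form requirement while they remain non-serious and within the description in 10.1, unless the participant complains.

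**Step 4: do the questionnaires fill the gap?** In part. Visits fall before and after each 7-day intervention, so a past-week score taken afterwards covers that intervention. The GSRS and ACQ as reproduced in the appendices have no field for onset, relatedness, action taken or outcome. Asthma control is a listed secondary outcome; the GSRS is not listed in section 6.4 or the synopsis.

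**Step 5: severe or serious?** *Severe* in 10.1 is not defined and goes to one recipient; *serious* in 10.2 is defined and goes to three. Because 10.1 points to 10.2 and the deadline is the same, this is a minor inconsistency.

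**The case against.** The strongest defence is that the trial collects more than these two rules suggest, and much of it stands.

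- **Staff do not ask only about supplement effects.** The phone question under Study Visits is open. It covers intervention-phase calls only, and 10.1 contradicts it for those same calls.
- **The symptoms are measured.** The GSRS and ACQ record gastrointestinal symptoms, wheeze and reliever use at visits 2–7, under blinding and attributable to a treatment period. A reader might infer that these symptoms go unrecorded; they do not. What is missing is their entry as AEs.
- **Intense effects are not clearly excluded.** Section 10.1 foresees mild, short-lived gastrointestinal effects and minor chest discomfort. Something worse or longer can reasonably be called unforeseen, and a serious event goes on the SAE Form in any case. The text does not support saying that these effects escape the form whatever their intensity.
- **Asthma worsening is not a listed foreseen effect.** The foreseen wheeze is the reaction to saline. Deterioration of asthma can therefore qualify for the AE Form. The weakness there is the visit question, not the form rule.
- **Complaints also go on the form.** This may bring in some foreseen symptoms, but only those volunteered, and the clause can equally be read as meaning grievances about the research.
- ***Unforeseen* may have been meant for ethics reporting alone.** That is plausible, but the sentence applies the word to documentation too. If this was the intent, the fix below merely states it.
- **Form fields and AE tables are often left to the CRF and the analysis plan.** True, and their absence is not criticised here. The point concerns rules that this protocol does state and that disagree.

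**Conclusion.** The point holds in a limited form. The definition in 10.2, the enquiry rules in 10.1 and Study Visits, and the form rule in 10.2 do not match. Followed as written, foreseen non-serious effects need not enter the AE record, and the AE question at visits does not prompt for unrelated events. AE counts by treatment would be incomplete.

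The size cannot be put as a rate. The documents give no expected AE frequencies and specify no AE table, so any percentage of missed events would be invented. The countable part is the 11 named effects without a stated form requirement. The plasma SCFA analysis is untouched, and no tolerability comparison is among the aims. The consequence falls on any safety or tolerability statement drawn from AE counts.

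A reader might go further and infer that the AE record would be nearly empty, or would miss asthma deterioration altogether. The documents do not support that: the open phone question, the rule for unforeseen events and the reporting of all AEs to the principal investigator remain, and nothing forbids staff from recording more than is required.

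The conclusion assumes that staff apply the sections literally and that no separate form instruction, not shown here, already widens them.

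**What to change.** 1. **Section 10.1, enquiry.** Replace the supplement-related question with an open, causality-neutral one at every visit and call, for instance about any new or worsened symptom or illness since the last contact. Make it consistent with Study Visits. Have relatedness judged afterwards by an investigator who remains blinded.
2. **Section 10.2, recording.** Require the AE Form and CRF for every AE that meets the definition, foreseen or not, with its treatment period. Onset, intensity, relatedness and outcome should be recorded with it. Keep *unforeseen* only as the trigger for reporting non-serious AEs to the ethics committee.
3. **Sections 10.1 and 10.2, expedited reporting.** Reconcile *severe* with *serious*, and the two lists of recipients.

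The cost is a few sentences in two sections and more form entries at contacts already scheduled. No visit, test or participant is added. Recorded tolerability may look less favourable, because expected mild effects will now be counted.
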